8.2 Secondary objectives

In addition, present study aims to determine the risk of addiction/ abuse and hospital admissions among opioid users with chronic non-cancer pain compared to patients with non-opioid pain medication.

The secondary objectives will be addressed with following hypotheses:

- How often do patients on long-term opioid therapy and patients with non-opioid pain medication being hospitalized and how long do they stay in hospital?
- Does the number of hospitalizations and length of stay in hospital differ between patients on long-term opioid therapy compared to patients with non-opioid pain medication in time period of five years?
- How many misuse and addiction diagnoses were coded in outpatient sector for patients on long-term opioid therapy and patients with non-opioid pain medication in time period of five years?
- Does the number of outpatient misuse and addiction diagnoses differ between patients on long-term opioid therapy compared to patients with non-opioid pain medication in time period of five years?
- How many sick leave days do patients on long-term opioid therapy and patients with non-opioid pain medication have in time period of five years?

9. Research Methods

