9.2 Setting and Study Population

The database contains data on around 4 million insured people from 69 German statutory health insurances (SHI). German SHI system comprises of approximately 120 independent health insurance companies. Funds paid by these SHI to any provider of health care (e.g. hospitals, physicians, pharmacies, psychotherapists and physiotherapists) represent almost the complete picture of the total health care costs of individual patients. All health insurance data can be linked to patients' demographics including age and gender. Health care data in the database include:

- Patient demographics:
 - age
 - gender
 - date of death

- region of residence
- insurance status
- date of insurance start and end
- Hospital care:
 - main diagnosis (ICD-10-GM codes) and additional diagnoses
 - procedures and surgeries
 - date of hospital admission
 - reason for admission (e.g. accident, emergency, normal)
 - date of end of hospital stay
 - reason of end of hospital stay (e.g. regular discharge from hospital, death)
 - DRG-Code
 - costs
- Outpatient care:
 - diagnoses (ICD-10-GM codes)
 - quarter in which the diagnosis was documented
 - procedures performed (EBM codes, e.g. laboratory tests, radiology, echocardiography) and date of procedure
 - type of specialist that documented the diagnosis and performed the procedure (e.g. cardiologist, general practitioner)
 - costs
- Pharmaceutical claims:

- drug dispensed (PZN code, which identifies medications at the package level) – this is mapped to ATC codes and DDDs
- quantity dispensed
- day of prescription
- day of dispensing
- type of specialist prescribing the medication (e.g. general practitioner)
- costs of drugs dispensed from the perspective of the statutory health insurance (without individual rebates between insurance and pharmaceutical companies)
- Physical therapy and technical aids:
 - type of therapy (e.g. massage, occupational therapy, walker, wheel chair)
 - quantity prescribed
 - type of care provider
 - start and end date
 - costs
- Sick leave:
 - diagnoses that cause sick leave
 - duration of sick leave
 - start date of sick leave
 - end date of sick leave

- type of specialist that filled out the sick leave form (e.g. general practitioner)
- costs of sick leave

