To note, data are adjusted within the database to Germany's typical age and sex distribution in accordance with the Federal Statistical Office based on the year 2013 (<https://www-genesis.destatis.de/genesis/online>) to foster its overall representativeness in regards to the population in Germany. Privately insured patients in Germany are not included in this database.

All data used are explicitly approved by the involved statutory health insurances for health care research usage according to § 287 or § 75 of the German social security law (SGB V).

Source population of the study are patients covered by the German Health Claims database over 2012-2017 years.

Study population are patients from the source population meeting inclusion (eligibility) criteria (see section 9.2.2).

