9.3 Risk adjustment

9.3.1 Propensity Score Matching

For the planned analyses, patients with opioid and non-opioid treatment need to be comparable. Mortality rates are expected around 100 and 200 per 10,000 persons years⁸ thus limiting the number of covariates for risk-adjustment to avoid over-fitting (10:1 rule of thumb: Not more than 1 predictor/covariate for 10 events). To avoid this overfitting problem but still be able to adjust for a large number of covariates, a propensity score (PS) matching will be conducted before the acutual Cox regression.

PS-Matching will be based on logistic regression and reflect the probability of getting an opioid treatment considering the following risk factors. The choice of covariates is based on a previous retrospective cohort study about opioid dependency and mortality in the US⁹ (see Appendix A, for the list of study covariates based on Ray et al.)

- region (i.e. 'Bundesland')
- comorbidities: obstructive sleep apnoea, depression and other comordidities
- comedication with other anticonvulsants than gabapentin, pregabalin or carbamazepine, comedication with neuroleptics, NSAR, tranquilizer or muscle relaxants, metamizole, comedication

⁸ Numbers from Ray et al. (2016)

⁹ Ray et al., 2016

with cannabinoid drugs, year of index treatment and drug dosage of the opioids/non-opioids as defined in section 9.4.

- medical procedures based on OPS-codes assessed as a number of procedures (see Appendix B, for the list of OPS codes), e.g. dialysis

PS matching will be based on a logistic regression (logit model) and reflects the likelihood that a patient will be prescribed by opioid medication if certain risk factors/comorbidities are considered. All binary predictors are included in the model as dummy variables (1 vs. 0). The influence of each variable is given as odds ratios with 95% confidence intervals.

The following equation will be employed for PS matching:

$$P_i = \frac{e^{\beta_0 + \sum_{j=1}^n \beta_j x_{j,i}}}{1 + e^{\beta_0 + \sum_{j=1}^n \beta_j x_{j,i}}}$$

The dependent variable is the treatment and will be dummy coded as 1 (opioid treatment in index year) and 0 (no opioid treatment) (P_i).

Age and gender will also be used for risk adjustment and will be assessed using national insurance data, for age by date of birth and is calculated based on the index treatment. For age, a variance of 5 years is allowed, i.e. the age can vary by plus / minus 5 years when matching.

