9.4.2.2 Secondary endpoints

Secondary endpoints are following:

- **Hospitalization due to any course.** Hospitalization will be assessed via the number of hospitalisations (calculated by counting the number of discharge dates (KH_Fall. Entlassungsdatum) in the year of interest, hospitalization rate, and length of stay in the hospital (KH_Fall. Verweildauer). The rate of hospitalization will be estimated as the number of patients with at least one hospitalization during the follow-up period divided by person-time of follow-up, censoring at time of death, last known record for the patient in the database, or 31st December 2017 (end of latest data cut), whichever is earlier.
- **Intensive care unit (ICU-stay)** stay is defined as patient's stay based on specialty of department in hospital (KH_OPS.Fachabteilung = 3600).
- **Hospitalization with to misuse or addiction.** The hospitalization with misuse or addiction will be analysed, if principal (main) diagnosis at discharge date between January 1st 2013 and December 31st 2017 contains at least one ICD-10 diagnosis of misuse/addiction: F10* or F11* or F13* or F19* or T40* (see also Appendix B in **Fehler! Verweisquelle konnte nicht gefunden werden.**).
- **Hospital admission diagnoses.** We report the hospital admission diagnoses based on ICD-10 codes between January 1st 2013 and December 31st 2017.
- **Coding of procedures in hospitals** that indicate number of patients that were hospitalized with severe diseases such as cardiovascular

diseases will be assessed via OPS-Codes provided in Appendix B as an excelsheet.

- **Coding of a misuse or addiction diagnosis in the outpatient sector** will be assessed via number of codings of misuse/addiction (ICD Codes = F10* or F11* or F13* or F19* or T40*) in outpatient sector by general practitioner or a specialist (e.g. psychiatrist), as ensured diagnosis (Diagnosesicherheit='G'). Additionally, the number of patients with a least one coding of ICD 10 codes of an ensured misuse/addiction in outpatient sector by general practitioner or a specialist (e.g. psychiatrist) will be assessed.
- **Sick leave** will be assessed as an absolute number and relative frequencies of patients with an attest of inability to work (patients with attest of inability to work as a percentage of all patients) in 2013-2017 and number of days being off work.
- **Hospital deaths** will be assessed via reason of discharge = death (Entlassgrund = Tod)

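### The sick-leave percentage is taken over all patients, including people outside the workforce, so it understates sick leave among those in work and depends on the share in work

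*Protocol*

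**What the plan says.** Protocol section 9.4.2.2 defines sick leave by the absolute number and relative frequency of certified patients, the latter as "patients with attest of inability to work as a percentage of all patients". The period and the second measure follow directly: "in 2013-2017 and number of days being off work". No at-risk population is named for either measure.

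The research question in section 8.2 is "How many sick leave days do patients on long-term opioid therapy and patients with non-opioid pain medication have in time period of five years".

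The population is wide. Section 9.2 states that "data are adjusted within the database to Germany's typical age and sex distribution" and that "Study population are patients from the source population meeting inclusion (eligibility) criteria". Those criteria (sections 9.2.2.1 and 9.2.2.2) concern drugs, pain diagnoses, earlier therapy, cancer treatment, palliative care and opioid substitution. None concerns age or employment.

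On adjustment, section 9.3.1 uses age and gender in addition to the propensity covariates, and "the age can vary by plus / minus 5 years when matching". The covariates named there are region, comorbidities, comedication, index year, dosage and procedures. Section 9.2 lists "insurance status" among the available fields, but the sick-leave endpoint does not use it.

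**The concern.** A sick-leave certificate is an event for people who have work to be absent from. Dividing by everyone combines two quantities, how many patients are in work and how often those in work are certified sick. The reported percentage cannot separate them.

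Two things are at stake. First, the level in each cohort will look lower than the sick leave that working patients with chronic pain experience. Second, the results for the two cohorts will stand side by side. If one cohort has more pensioners or other people outside the workforce, it will show less sick leave even when working patients are certified equally often. A real difference among working patients can be hidden in the same way.

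**Working it through.** The protocol gives no sick-leave rate, employment share or sample size for this endpoint, so there is no figure to reproduce. The check has a textual part and an arithmetic part.

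**Text: who is in the denominator?**

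- Section 9.4.2.2 fixes it as all patients.
- Sections 9.2.2.1 and 9.2.2.2 set no age or employment limit.
- Section 9.2 ties the source data to the age structure of the whole German population, and Table 9-4 lists age above 65 as a risk factor. Patients past working age are therefore expected.
- The limitations in section 9.10 do not mention the point.

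**Arithmetic: what does the percentage measure?**

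Let w be the share of a cohort in work and r the risk of at least one certificate among those in work. Assume that people outside work receive none (the protocol does not say who is entitled). Then

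all-patient percentage = w × r,

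and the ratio of cohort 1 to cohort 2 is (w₁ × r₁) / (w₂ × r₂). If the risk is equal (r₁ = r₂), this reduces to w₁ / w₂. All values of w and r below are assumptions.

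| Share in work, cohort 1 vs 2 | All-patient %, r = 40% in both | All-patient %, r = 60% in both | Ratio |
|---|---|---|---|
| 50% vs 50% | 20.0 vs 20.0 | 30.0 vs 30.0 | 1.00 |
| 45% vs 50% | 18.0 vs 20.0 | 27.0 vs 30.0 | 0.90 |
| 40% vs 50% | 16.0 vs 20.0 | 24.0 vs 30.0 | 0.80 |
| 30% vs 50% | 12.0 vs 20.0 | 18.0 vs 30.0 | 0.60 |

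Example for the third row: 0.40 × 0.40 = 0.16 and 0.50 × 0.40 = 0.20, so the ratio is 0.16 / 0.20 = 0.80. The true ratio among those in work is 1.00 in every row.

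*Level.* In the first row the comparison is unaffected, but a risk of 40% among workers is reported as 20%, half its value.

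*Masking.* With risks of 50% vs 40% among those in work and shares in work of 40% vs 50%, the figures are 0.50 × 0.40 = 20% and 0.40 × 0.50 = 20%. A true ratio of 0.50 / 0.40 = 1.25 is reported as 1.00.

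*Days off work.* If days are averaged over all patients, the mean is w times the mean among those in work, and the same dependence applies. The protocol does not say how days will be averaged.

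**After restriction.** With the denominator limited to those who can receive a certificate, w drops out. The figures become 40% vs 40% or 60% vs 60%, ratio 1.00, in every row.

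**Does matching equalise w?** Matching on age and gender narrows a gap in employment. Whatever retirement age applies, two patients up to 5 years apart can fall on either side of it, and people of the same age can differ in early retirement or disability pension. The gap is reduced but not necessarily closed.

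**The case against.** The strongest case on the other side is that this is a clearly defined descriptive measure of burden in the whole cohort, reported next to the absolute number and the days off work. Section 8.2 asks whether the cohorts differ for hospitalization and for outpatient misuse diagnoses, but for sick leave it asks only how many days there are. Section 9.7.1 assigns the t-test and Chi² test to questions about differences, and the synopsis does not list sick leave among the secondary endpoints. This stands, and it limits the weight of the point.

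Readers might draw four stronger conclusions that the protocol does not support:

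- *That the plan will produce a false benefit for one cohort.* This needs a gap in employment that remains after matching, and its direction. The protocol shows neither. Comorbidity and procedure covariates may also partly balance exit from work for health reasons.
- *That employment is certainly absent from the propensity model.* The covariate list in Appendix A is not available here, so it cannot be ruled out. Such a covariate would help the comparison but would leave the denominator unchanged.
- *That leaving out time at risk for days off work is an error.* The protocol fixes no denominator for days, and that detail is commonly left to a statistical analysis plan. It belongs in the remedy and is not a fault.
- *That the remedy is a simple filter with censoring at retirement.* Section 9.2 only names the insurance field. It does not say that the field identifies employed members or dates changes of status.

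What survives is that the denominator is written down as all patients and that nothing else in the protocol limits it to people who can have the event.

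**Conclusion.** The point holds as a minor one. The stated denominator dilutes sick leave among working patients in both cohorts, and a side-by-side reading depends on how similar the cohorts are in the share in work. The first effect follows directly from the definition, provided that people outside the workforce are included and do not receive certificates. The second requires a residual difference in employment after matching, which is plausible but not shown.

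The size cannot be determined from the protocol. With equal risk, the spurious ratio runs from 1.00 (no gap) through 0.90 (45% vs 50% in work) to 0.60 (30% vs 50%), and it would exceed 1 if the gap ran the other way. These shares are illustrations, not estimates. The primary endpoint and every question that asks for a difference between the cohorts are unaffected.

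**What to change.** In section 9.4.2.2, keep the all-patient percentage and add beside it the percentage certified and the days off work among patients who can receive a certificate at index. Define that group by insurance status if the field is confirmed to identify employed members, and otherwise by a working-age restriction. Report the size of this denominator for each cohort, so that a difference in the share in work is visible. Express days per person-year of follow-up, in line with the person-time already used for mortality and the hospitalization rate.

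Do not censor at retirement. The protocol does not show that retirement is dated, and leaving work may itself result from pain or treatment, so such censoring could be informative and remove the most affected patients.

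The cost is a smaller group for this endpoint and some extra analysis of data already held. A working-age restriction would be only approximate, because it keeps people of working age who are not employed.

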9.5 Validity and Reliability

The external validity of the used data set is checked against the national reference data from official resources: Information System of the Federal Health Monitoring for the total German population and from the German Drug Prescription Report for the German population insured within the SHI system (Anderson et al., 2016). The reliability of each outcome variable (i.e., diagnoses) will be warranted due to the use of only “ensured”

(instead of suspected diagnosis) outpatient diagnoses or inpatients diagnoses.

9.6 Data Management

9.6.1 Obtaining Data Files

The data authority of the involved statutory health insurance (SHI) will obtain the data based on this analytical protocol. There will be an approval process of the data used and the methods applied. The involved SHIs will therefore get a copy of this analytical protocol to review whether the issues addressed are for health care research only.

9.6.2 Linking Data Files

Not applicable.

9.6.3 Review and Verification of Data Quality

The frequency of missing data will be provided for each variable in the output tables. Range (min and max) will be reported in order to find implausible low or high values for each continuous variable in the analysis.

9.7 Data Analysis

All analysis will be conducted using R (version 3.3.1 or subsequent versions) and the SAS Statistical Package 9.4 .

Main analysis will focus on each of the 2 main cohorts as defined at inclusion:

- Patients with pain diagnosis and opioid treatment between 1st January 2013 and 31st December 2017

- Patients with pain diagnosis and non-opioid treatment between 1st January 2013 and 31st December 2017

Stratified analyzes will be carried out for each of the 2 main sub-cohorts and each following pain conditions will be conducted: headache (R 51*); pain, not elsewhere classified (R52*); persistent somatoform pain disorder (F45.4*); polyneuropathy in diabetes (E10.4*-E14.4 plus G63.3).

9.7.1 Planned Analyses

To address the main research questions, descriptive analyses, Cox proportional hazards regression and test for examining group differences (T-test and Chi² test) will be provided.

Descriptive analyses using mean, median, standard deviation, absolute and relative frequency, minimum and maximum will be reported.

To address the research questions about the differences between opioid and non-opioid treatment, inductive analyses using Chi² Tests and t-test with critical value at the 5% significance level will be employed.

9.8 Subgroup and Sensitivity Analysis

9.8.1 Subgroups for additional descriptive analyses

The following main sub-groups of patients will be distinguished to stratify during descriptive analyses while assessing study objectives:

Subgroup analyses for each following pain conditions will be conducted:

Subgroup
Headache (R 51*)
Pain, not elsewhere classified (R52*)

Persistent somatoform pain disorder (F45.4*)
Polyneuropathy in Diabetes (E10.4*-E14.4 plus G63.3)
Back pain (M54*)
Arthrosis (M15*-M19*)

9.8.2 Sensitivity analysis

The following main sensitivity analysis will be conducted:

Sensitivity analysis
No cancer patients: Exclude all patients with at least one C00 – C96 diagnosis before index date

9.9 Quality Control

Assessment of availability and completeness of variables, including missing data and implausible ranges, as described in previous sections, will be conducted.

9.10 Limitations of the Research Methods

9.10.1 Internal Validity of Study Design

The statutory health insurances database uses billing data which are designed for invoices and not for research activities, and therefore lack detailed clinical information and lab data. About 10% of German inhabitants are members of the private health insurance companies.

Because the access to a private health insurance companies in Germany has special requirements, among others income, there are differences between insured patients of statutory and private health insurance

companies in terms of their socioeconomic status and health (care) behavior. Therefore the study sample may not be completely representative of the general German population in terms of socioeconomic status.

Given the data structure of the German health care system, the exact treatment dosage of a medication has to be estimated and might differ from the real dosage. There is also no clinical patient information and we do not know whether the dispensed drugs were used immediately, saved for later use, diverted or not used at all. The assumption that all drugs were used at a time close to dispensation would probably lead to an overestimation of drug use.

9.10.1.1 Measurement Error(s)/Misclassification(s)

Due to administrative nature of the database, the possibility of misclassification and miscoded data exists. This study is using prescription data to assess possession, which is only a proxy for patients taking their medication. There may be missing data due to limitations of the linkage between different datasets, with fully linked data available for subsets of patients.

9.10.1.2 Information Bias

There is a potential for misreporting of information in the existing health systems from where data are retrieved (medical records and national health registries). However, due to a large sample size in present study, an error in classification of a condition would unlikely to have a significant effect on final results. The current study focuses on deaths and

hospitalisations as key outcome measures that are less likely to be missing and less likely to be subject to bias.

9.10.1.3 Selection Bias

All eligible patients who meet inclusion criteria will be considered for the analysis. The selection bias is less likely in claims data of health insurances data.

9.10.1.4 Confounding

Confounding occurs when a covariate is independently associated with the exposure and the outcome of interest. The size of the datasets should allow analysis to explore and control this bias satisfactory. Subgroup analyses of subpopulations with different chronic pain diagnoses will be considered. However, unmeasured confounding cannot be excluded.

9.10.2 External Validity of Study Design

External validity describes the degree to which findings are able to be generalizable to the total population. Due to the retrospective observation design, the present study shows benefits of interventions under real conditions and increases the external validity. Insurees contributing to the German statutory health insurances are broadly representative of the German general population, although given these were originally employer based sickness funds, it is possible there are some residual differences in the demographic profile. Also, as indicated in section 9.9.1, private insurance patients (about 10% of German population) are not covered in this database. The demographic profile of

covered patients will be compared with general population demographics as far as data allow.

